5. BACKGROUND

Endometrial cancer is a surgically staged disease. Staging involves removal of the uterus, tubes and ovaries as well as lymph nodes in the pelvic and aortic regions. In women with cancer that does not invade the uterine muscle or is of low grade and invades less than 50% of the muscle, removal of the lymph nodes is not mandatory. Intraoperative evaluation of the depth of invasion of the cancer is critical, therefore, in determining which patients require lymphadenectomy. Gross visualization is highly inaccurate. It is more sensitive to obtain a pathological frozen section on the uterus to accurately diagnose depth of invasion. However, frozen section increases the operative time and incurs an additional expense for the procedure. A rapid and accurate intraoperative assessment of invasion which could be performed in the operating room would reduce the time and expense of a frozen section. We propose to utilize fluorescein dye given intravenously prior to the hysterectomy to aid in visually determining the depth of invasion. If this assessment correlates well with the pathologic depth of invasion, then this could represent a valuable intraoperative tool to determine which patients require lymphadenectomy.

Fluorescein is approved by the FDA for angiography of the retinal vessels. There are many procedures that utilize fluorescein beyond its FDA indication. It is commonly used during surgery to assess the vascular viability of tissue, most particularly the viability of the intestines when there is concern. In this situation, fluorescein is injected intravenously and the intestines are examined using a Woods lamp to detect the areas of fluorescence. Areas of poor vascularity will not fluoresce. It is also commonly used to detect the boundaries of skin lesions. For example, in assessment of vulvar Paget's disease fluorescein injection and visualization of the vulva with Woods lamp can detect the extent of the lesion that would otherwise not be detectable by the naked eye.

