14. STATISTICAL CONSIDERATIONS

- a. Sample Size and Study Duration:** 100 subjects will be entered into this pilot study. It is estimated that this study will be completed in less than one year.

- b. Study Endpoints:** Invasion depth as determined using each of three methods: Systemic Fluorescein Injection (SFI), Frozen Section (FS), and Permanent Section (PS).
- c. Data Analysis Plan:** The primary objective is basically to determine whether the SFI method works. Provided that it works, the analysis plan in support of the Secondary Objective is as follows: For each study subject, the paired difference in invasion depths determined using the SFI versus FS methods will be calculated and expressed as a percentage of the FS-based invasion depth. Likewise, the paired difference in invasion depths determined using the SFI versus PS methods will be calculated and expressed as a percentage of the PS-based invasion depth. Each type of paired difference will be summarized as the mean and standard deviation. Because PS is considered the definitive “gold standard” of determining invasion depth, the mean of the paired differences between SFI and PS methods will be compared against equivalence limits of -25% and $+25\%$ via the Two One-Sided Tests (TOST) procedure using an $\alpha=0.10$ significance level. If this mean is significantly “in between” both equivalence limits, then this will indicate that the discrepancy in invasion depths between SFI and PS is significantly less than 25% , and we will accordingly consider further investigation of the SFI method of determining invasion depth.

Sample Size and Power: When two methods are equivalent, the mean of their paired difference will be 0% . The power of the TOST procedure to declare that a mean of 0% is significantly “in between” equivalence limits of -25% and $+25\%$ depends heavily on the standard deviation of the paired difference when the sample size is fixed at 20 subjects. A simulation study using 1,000,000 simulations in PASS 12 software indicates that 20 subjects gives the TOST procedure $>90\%$ power at 10% alpha to declare a mean of 0% to be significantly “in between” the above-stated equivalence limits provided that the standard deviation of the paired differences is less than 37% . This power calculation shows that, if SFI agrees well with PS, then 20 subjects should provide our study with sufficient power to demonstrate that fact.

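### A passing TOST bounds the average SFI–PS bias within ±25%, but the plan reads it as the discrepancy itself being below 25%

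*Combined protocol and SAP*

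**What the plan says.** Under Data Analysis Plan in section 14c, each subject's SFI–PS difference keeps its sign and is divided by the PS depth. Then "the mean of the paired differences between SFI and PS methods will be compared against equivalence limits"; those limits are −25% and +25%, and the method is TOST at α = 0.10. The plan gives its reading of a mean that falls significantly between the limits: "then this will indicate that the discrepancy in invasion depths between SFI and PS is significantly less than", with 25% as the figure. The only step it attaches to a pass is this: "we will accordingly consider further investigation of the SFI method of determining invasion depth".

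Scatter appears in two places. It is described: "Each type of paired difference will be summarized as the mean and standard deviation". It also enters the power paragraph as a condition, an SD below 37%. That paragraph closes: "This power calculation shows that, if SFI agrees well with PS", twenty subjects are enough to demonstrate it.

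Section 5 gives the purpose. "If this assessment correlates well with the pathologic depth of invasion", SFI might serve during surgery to identify who needs lymphadenectomy.

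**The concern.** A mean of signed differences measures average bias. A subject read 40% too deep and another read 40% too shallow contribute a mean of zero between them. A test on that mean cannot support a statement about how far SFI lies from PS in a given subject, yet discrepancy and good agreement are the words the plan attaches to a pass.

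The use foreseen in section 5 is a decision for each patient, so a reader will take the conclusion to mean closeness in individuals. Nothing in the plan sets a limit on scatter or asks how many subjects have an SFI reading close to PS. A method that is right on average and wide of the mark in most patients could be reported as agreeing with the gold standard, and the next study would be planned on that footing.

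**Working it through.** **Inputs from section 14.** Limits ±25%; α = 0.10; true mean difference 0%; SD ceiling 37%; N = 20 in the power paragraph and 100 in 14a. The documents give no expected SD and no distribution, so those below are assumptions.

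**1. The plan's power figure.** The test passes if the mean ± t(0.90, N−1) × s/√N lies inside ±25. By simulation, N = 20 and SD 37% give 90.6%, falling to 88.9% at SD 38%. The stated figure of more than 90% therefore reproduces with α = 0.10 for each one-sided test; 0.05 for each gives 79.5%.

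**2. Subjects beyond ±25% (normal differences, mean 0).** Share = 2 × [1 − Φ(25/SD)].

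| SD | Share beyond ±25% |
|---|---|
| 20% | 21.1% |
| 25% | 31.7% |
| 30% | 40.5% |
| 37% | 49.9% |
| 50% | 61.7% |

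At SD 37% the nominal 95% limits of agreement are ±1.96 × 37 = ±72.5 points. Looking only at trials that pass hardly changes this: among simulated trials of 20 that pass, on average 49.3% of subjects are beyond ±25%. For 95% of subjects to lie within ±25%, the SD would have to be 25/1.96 = 12.8%.

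**3. Without normality.** A percentage difference cannot fall below −100%, so the normal model is only illustrative. As an alternative, take SFI/PS as lognormal with mean 1 and coefficient of variation CV: s² = ln(1 + CV²), μ = −s²/2. With CV = 0.37 and N = 20, the test passes 90.4% of the time, 47.8% of subjects are beyond ±25%, and the central 95% range is −53.5% to +89.3%.

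**4. The enrolled number.** At N = 100 and an assumed SD of 50%, the test passes 99.98% of the time with 61.7% of subjects beyond ±25% (normal), or 99.9% with 59.4% (lognormal).

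**5. How far the standard error restrains scatter.** With an observed mean of 0, the test fails only if s exceeds 25 × √N / t(0.90, N−1). That is 84.2% at N = 20 and 193.8% at N = 100.

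**6. A counterexample to the inference.** Let half the subjects read 50% too deep and half 50% too shallow. The mean is 0. At N = 20 the sample SD is 51.3 and the 80% confidence half-width 15.2; at N = 100 they are 50.25 and 6.5. Both pass, and no subject is within 25% of PS.

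**The case against.** The sentence in question opens by referring to the mean, so discrepancy can be read as mean discrepancy, and on that reading the inference is valid. This has force, but the close of the power paragraph speaks of SFI agreeing with PS, which is wider than average bias. If mean bias is all that is meant, saying so costs nothing.

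The 37% is a ceiling for the power statement, not an expected SD, and the share beyond ±25% falls at smaller values. This stands: about half is what can happen at the edge of the plan's condition, not a forecast. Even at SD 25%, nearly a third of subjects are outside under the normal model.

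The two-point example and the SD ceilings of 84% and 194% are extreme. They are, and they show only what the rule permits.

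The SD will be reported, so nominal limits of agreement can be worked out from planned output. That is true, but no criterion attaches to the SD and the written decision rule does not use it beyond the standard error.

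The ±25% margin was set for a mean, and section 5 ties node removal to the absence of invasion or, with low grade, to invasion of less than half the muscle. A subject can be within ±25% of PS and on the wrong side of that line, or the reverse. This also stands. The proportion within ±25% measures the closeness that the plan's sentence claims; it does not measure correct classification at 50%.

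Finally, this is a single-arm pilot and the test serves a secondary objective. Frozen and permanent sections are done regardless. That limits the severity but leaves the inference unsupported.

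**Conclusion.** The concern holds. A significant TOST here supports one statement, that the mean SFI–PS difference is within ±25%. It does not support the plan's statement about the discrepancy. The counterexample establishes this without any distributional model. The size depends on the unknown SD: with a true mean of 0, about half of subjects are beyond ±25% at SD 37% under either the normal or the lognormal assumption, and about a fifth at SD 20% under the normal.

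The plan should be corrected, but no treatment decision in this trial rests on it. The harm is a misleading conclusion and a weak basis for the next study.

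**What to change.** Keep the TOST. In section 14c, restate its conclusion as: the mean bias of SFI relative to PS is within ±25%. Then add, from depths already recorded:

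1. Bland–Altman 95% limits of agreement for SFI–PS with confidence intervals, or the 2.5th and 97.5th percentiles if the differences are clearly skewed.
2. Among subjects with PS depth above zero, the proportion whose SFI reading is within ±25% of PS, with an exact 95% confidence interval.
3. For subjects with PS depth zero, their number and SFI depths, reported separately because a percentage of zero is undefined. Section 5 recognises such disease: "In women with cancer that does not invade the uterine muscle", node removal is not mandatory.

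Weigh these results alongside the TOST when deciding on further investigation. Any minimum proportion is for the sponsor to set before data are seen.

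Precision is useful at 100 subjects. If 90 of 100 are within ±25%, the exact interval is 82% to 95%. If only 70 have PS depth above zero (an assumption), 63 of 70 gives 80% to 96%. The interval for each limit of agreement has half-width t(0.975, N−1) × SD × √[1/N + 1.96²/(2(N−1))]; at SD 37% this is 12.6 points at N = 100 and 30.1 at N = 20.

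The cost is a change of wording and a small added analysis, with no new data. The conclusion may be less favourable if scatter is wide.

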15. ETHICAL AND REGULATORY CONSIDERATIONS

The following must be observed to comply with FDA regulations for the conduct and monitoring of clinical investigations. The following also represents sound research practice. All study personnel must have completed training in good clinical practice (GCP) and protection of human subjects.

- a. Recruitment and Informed Consent:** Patients with endometrial cancer will be identified in the UAMS gynecologic cancer clinic during routine clinic appointments by their providers. Upon identification, the patient will be informed of the study by their physician along with the research staff. The patient will be allowed to review the IRB-approved informed consent form, and if they would like to participate in the study, they will be presented the informed consent form. During the consent process, the patient will be clearly informed of the fact that participation in this study is voluntary and that the decision to not participate in the study will have no effect on future clinical care. The patient will be encouraged to have family or

friends participate in any or all of the process. The patient will be provided sufficient time to ask questions, and will be questioned to ensure they understand the information. If the patient agrees to proceed, they will sign consent. The consent process will be documented in the medical record. A copy of the informed consent document will be given to the research participant, and additional copies will be sent to the medical records department. The original informed consent will be filed with the subject file in CCTO. The principles of informed consent are described by the Federal Regulatory Guidelines: Code of Federal Regulations (21CFR50) and the Office for Human Research Protections: Protection of Human Subjects (45CFR46). These principles must be followed to comply with Food and Drug Administration (FDA) regulations for the conduct and monitoring of clinical investigations.

- b. Institutional Review:** This study will be approved by the UAMS Institutional Review Board (IRB) as defined by Federal Regulatory Guidelines 21CFR56 and the Office for Human Research Protections: Protection of Human Subjects 45CFR46. This study will also undergo scientific review by the Cancer Institute's Protocol Review and Monitoring Committee (PRMC). Approval by both the IRB and PRMC is required before the clinical trial can be activated.
- c. Investigational Agent Accountability:** Fluorescein for this study will be stored in the main inpatient pharmacy and will be ordered from there and sent to the operating room pharmacy for pick up. Fluorescein dye will be purchased by Pharmacy for this study, and the Division of Gynecologic Oncology will reimburse pharmacy as subjects complete the study.

16. ADVERSE EVENTS

a. Expedited Reporting:

- The Principal Investigator (PI) must be notified within 24 hours of learning of any serious adverse events (SAEs), regardless of attribution, occurring during the study.
- The UAMS IRB must be notified within 10 business days of "any unanticipated problem involving risk to subject or others (UPR/UPIRTSO)."
- For UPR/UPIRTSO, see UAMS IRB Policy 10.2.

b. Routine Reporting: All other AEs, such as those that are expected, or are unlikely or definitely not related to the study participation, are to be reported annually as part of regular data submission.

17. MONITORING

- a. Medical Monitor:** The Medical Monitor, Principal Investigator and study staff will meet quarterly, once the PI has monitored the data, to review safety data (adverse events, serious adverse events and other scientific observations).
- b. Data Monitor:** The study will be monitored by the Principal Investigator to ensure that the rights and well-being of human subjects are protected, that the data are accurate, complete

and verifiable from source documents and that the trial is conducted in compliance with currently approved protocol/amendments.

APPENDIX I

FLUORESCITE - fluorescein sodium injection, solution

Alcon, Inc.

DESCRIPTION

FLUORESCITE® (fluorescein injection, USP) 10% contains fluorescein sodium (equivalent to fluorescein 10% w/v). It is a sterile solution for use intravenously as a diagnostic aid. Its chemical name is spiro[isobenzofuran-1(3*H*), 9'-[9*H*]xanthene]-3-one, 3',6'-dihydroxy, disodium salt. The active ingredient is represented by the chemical structure:

376.27 MW

FLUORESCITE® (fluorescein injection, USP) 10% is supplied as a sterile, unpreserved, single-use aqueous solution, that has a pH of 8.0 - 9.8 and an osmolality of 572-858 mOsm/kg.

Active ingredient: fluorescein sodium

Inactive Ingredients

Sodium hydroxide and/or hydrochloric acid (to adjust pH), and water for injection.

CLINICAL PHARMACOLOGY

Mechanism of Action

Fluorescein sodium responds to electromagnetic radiation and light between the wavelengths of 465-490 nm and fluoresces, i.e., emits light at wavelengths of 520-530 nm. Thus, the hydrocarbon is excited by blue light and emits light that appears yellowish-green. Following intravenous injection of fluorescein sodium in an aqueous solution, the unbound fraction of the fluorescein can be excited with a blue light flash from a fundus camera as it circulates through the ocular vasculature, and the yellowish green fluorescence of the dye is captured by the camera. In the fundus, the fluorescence of the dye demarcates the retinal and/or choroidal vasculature under observation, distinguishing it from adjacent areas/structures.

Pharmacokinetics

Distribution:

Within 7 to 14 seconds after IV administration into antecubital vein, fluorescein usually appears in the central artery of the eye. Within a few minutes of IV administration of fluorescein sodium, a yellowish discoloration of the skin occurs, which begins to fade after 6 to 12 hours of dosing. Various estimates of volume of distribution indicate that fluorescein distributes well into interstitial space (0.5 L/kg).

Metabolism:

Fluorescein undergoes rapid metabolism to fluorescein monoglucuronide. After IV administration of fluorescein sodium (14 mg/kg) to 7 healthy subjects, approximately 80% of fluorescein in plasma was converted to glucuronide conjugate after a period of 1 hour post dose, indicating relatively rapid conjugation.

Excretion:

Fluorescein and its metabolites are mainly eliminated via renal excretion. After IV administration, the urine remains slightly fluorescent for 24 to 36 hours. A renal clearance of 1.75 mL/min/kg and a hepatic clearance (due to conjugation) of 1.50 mL/min/kg have been estimated. The systemic clearance of fluorescein was essentially complete by 48 to 72 hours after administration of 500 mg fluorescein.

INDICATIONS AND USAGE:

FLUORESCITE® (fluorescein injection, USP) 10% is indicated in diagnostic fluorescein angiography or angioscopy of the retina and iris vasculature.

CONTRAINDICATIONS

FLUORESCITE® (fluorescein injection, USP) 10% is contraindicated in patients with known hypersensitivity to fluorescein sodium or any other ingredients in this product.

WARNINGS

FOR INTRAVENOUS USE

Care must be taken to avoid extravasation during injection as the high pH of fluorescein solution can result in severe local tissue damage. The following complications resulting from extravasation of fluorescein have been noted to occur: Sloughing of the skin, superficial phlebitis, subcutaneous granuloma, and toxic neuritis along the median curve in the antecubital area. Complications resulting from extravasation can cause severe pain in the arm for up to several hours. When significant extravasation occurs, the injection should be discontinued and conservative measures to treat damaged tissue and to relieve pain should be implemented. Rare cases of death due to anaphylaxis have been reported (See [PRECAUTIONS](#)).

PRECAUTIONS

General

Caution is to be exercised in patients with a history of allergy or bronchial asthma. An emergency tray should be available in the event of possible reaction to **FLUORESCITE®** (fluorescein injection, USP) 10%. Use only if the container is undamaged.

Information for Patients

Skin will attain a temporary yellowish discoloration. Urine attains a bright yellow color. Discoloration of the skin usually fades in 6 to 12 hours and usually fades in urine in 24 to 36 hours.

Laboratory Information

If a potential allergy is suspected, an intradermal skin test may be performed prior to intravenous administration, i.e., 0.05 mL injected intradermally to be evaluated 30 to 60 minutes following injection. Given the sensitivity and specificity of skin testing, a negative skin test is not proof that a patient is not allergic to fluorescein.

Carcinogenesis, Mutagenesis, Impairment of Fertility

There have been no long-term studies done using fluorescein in animals to evaluate carcinogenic potential.

Pregnancy

Teratogenic Effects: Pregnancy Category C

Adequate animal reproduction studies have not been conducted with fluorescein sodium. It is also not known whether fluorescein sodium can cause fetal harm when administered to a pregnant woman. Fluorescein sodium should be given to a pregnant woman only if clearly needed.

Nursing Mothers

Fluorescein sodium has been demonstrated to be excreted in human milk. Caution should be exercised when fluorescein sodium is administered to a nursing woman.

PEDIATRIC USE

Safety and effectiveness in pediatric patients have been established.

GERIATRIC USE

No overall differences in safety or effectiveness have been observed between elderly and other adult patients.

ADVERSE REACTIONS (SEE WARNINGS AND PRECAUTIONS)

Nausea, vomiting, gastrointestinal distress, headache, syncope, hypotension, and symptoms and signs of hypersensitivity have occurred. Cardiac arrest, basilar artery ischemia, severe shock, convulsions, thrombophlebitis at the injection site, and rare cases of death have been reported. Extravasation of the solution at the injection site causes intense pain at the site and a dull aching pain in the injected arm (see [WARNINGS](#)). Generalized hives and itching, bronchospasm and anaphylaxis have been reported. A strong taste may develop after injection.

DOSAGE AND ADMINISTRATION

The normal adult dose of **FLUORESCITE®** (fluorescein injection, USP) 10% is 500 mg (100 mg/mL) via intravenous administration.

For children, the dose should be calculated on the basis of 35 mg for each ten pounds of body weight (7.7 mg/kg body weight).

Parenteral drug products should be inspected visually for particulate matter and discoloration prior to administration. Do not mix or dilute with other solutions or drugs. Flush intravenous cannulas before and after drugs are injected to avoid physical incompatibility reactions.

Inject the dose rapidly (1 mL per second is normally recommended) into the antecubital vein, after taking precautions to avoid extravasation. A syringe, filled with **FLUORESCITE®** (fluorescein injection, USP) 10%, may be attached to transparent tubing and a 23 gauge butterfly needle for injection. Insert the needle and draw the patient's blood to the hub of the syringe so that a small air bubble separates the patient's blood in the tubing from the fluorescein. With the room lights on, slowly inject the blood back into the

vein while watching the skin over the needle tip. If the needle has extravasated, the patient's blood will be seen to bulge the skin and the injection should be stopped before any fluorescein is injected. When assured that extravasation has not occurred, the room light may be turned off and the fluorescein injection completed. Luminescence usually appears in the retina and choroidal vessels in 7 to 14 seconds and can be observed by standard viewing equipment.

Reduction in dose from 5 ml to 2 ml of **FLUORESCITE®** (fluorescein injection, USP) 10% may be appropriate in cases when a highly sensitive imaging system e.g., scanning laser ophthalmoscope is used.

HOW SUPPLIED

FLUORESCITE® (fluorescein injection, USP) 10% is supplied in a single-use 5 mL glass vial with a gray FluroTec coated chlorobutyl (latex free) stopper and purple flip-off aluminum seal. It contains a sterile, red-orange solution of fluorescein sodium.
NDC 0065-0092-65

Storage

Store at 2° - 25°C (36° - 77°F).

Do Not Freeze

Rx Only

ALCON LABORATORIES, INC.

Fort Worth, Texas 76134 USA

Printed in USA

© 2006, 2009 Alcon, Inc.

9004433-0209

PRINCIPAL DISPLAY PANEL

NDC 0065-0092-65 1 Dozen 5 mL Vials

Fluorescite® 10%

(fluorescein injection, USP) 10%

STERILE

100 mg/ml Fluorescein

Rx Only

FOR INTRAVENOUS USE

Store at 2° - 25° C (36° - 77°F)

Do Not Freeze

Alcon®

ALCON LABORATORIES, INC.

Fort Worth, Texas 76134 USA

©2000-2009 Alcon, Inc.

H11427-1009

NDC 0065-0092-65 1 Dozen 5 mL Vials

Fluorescite® 10%
(fluorescein injection, USP) 10%
STERILE
100 mg/mL Fluorescein
Rx Only
FOR INTRAVENOUS USE
Store at 2° - 25° C (36° - 77° F).
Do Not Freeze

Alcon®
ALCON LABORATORIES, INC.
Fort Worth, Texas 76134 USA

©2000-2009 Alcon, Inc. H11427-1009

MFD: EXP: LOT:

01110300650092651
